4.7 SAFETY ANALYSES

All safety analyses will be performed on the safety population as defined in [Section 3](#), unless otherwise specified, using the following common rules:

- The analysis of the safety variables will be descriptive, and no testing is planned.
- Safety data in participants who do not belong to the safety population (eg, exposed but not randomized) will be provided separately.

4.7.1 Extent of exposure

The extent of IMP exposure will be assessed by the duration of IMP exposure and compliance and summarized within the safety population.

Duration of IMP exposure

Duration of IMP exposure is defined as last dose date – first dose date + 14 days, regardless of unplanned intermittent discontinuations. Duration of IMP exposure will be summarized descriptively as a quantitative variable (number, mean, SD, median, minimum, and maximum). In addition, duration of treatment exposure will also be summarized categorically by numbers and percentages for each of the following categories and cumulatively according to these categories:

- >0 and \leq 2 weeks
- >2 and \leq 4 weeks
- >4 and \leq 8 weeks
- >8 and \leq 12 weeks
- >12 and \leq 16 weeks
- >16 and \leq 20 weeks
- >20 and \leq 24 weeks
- >24 weeks and \leq 24 weeks + 3 days
- > 24 weeks + 3 days

Additionally, the cumulative duration of treatment exposure will be provided, defined as the sum of the duration of treatment exposure for all participants, and will be expressed in participant years.

Treatment compliance

A given administration will be considered noncompliant if the participant did not take the planned dose as required by the protocol. No imputation will be made for participants with missing or incomplete data.

Percentage of treatment compliance for a participant will be defined as the number of administrations that the participant was compliant divided by the total number of administrations that the participant was planned to take from the first administration of IMP up to the actual last administration of IMP.

Treatment compliance will be summarized quantitatively and categorically: <80%, \geq 80%.

Cases of overdose (defined as at least twice the intended dose during an interval of less than 11 days) will be considered an AESI per dupilumab clinical programs and will be listed as such.

4.7.2 Adverse events

General common rules for adverse events

All adverse events (AEs) will be coded to a lower-level term (LLT), preferred term (PT), high-level term (HLT), high-level group term (HLGT), and associated primary system organ class (SOC) using the Medical Dictionary for Regulatory Activities (MedDRA) version currently in effect at Sanofi at the time of database lock.

The AEs will be analyzed in the following 3 categories:

- Pre-treatment AEs: AEs that developed, worsened or became serious during the pre-treatment period.
- Treatment-emergent adverse events (TEAE)s: AEs that developed, worsened or became serious during the treatment-emergent period
- Post-treatment AEs: AEs that developed, worsened or became serious during the post-treatment period

Similarly, the deaths will be analyzed in the pre-treatment, treatment-emergent and post-treatment periods.

The primary focus of AE reporting will be on TEAEs. Pre-treatment and post-treatment AEs will be described separately.

An AE with incomplete or missing date/time of onset (occurrence, worsening, or becoming serious) will be classified as a TEAE unless there is definitive information to determine it is a pre-treatment or a post-treatment AE.

If the assessment of the relationship to IMP is missing for an AE, this AE will be assumed as related to IMP. If the severity is missing for 1 of the treatment-emergent occurrences of an AE, the severity will be imputed with the maximal severity of the other occurrences. If the severity is missing for all the occurrences, the severity will be left as missing.

Multiple occurrences of the same event in the same participant will be counted only once in the tables within a treatment phase.

The AE tables will be sorted as indicated in [Table 6](#).

Table 6 - Sorting of AE tables

AE presentation	Sorting rules
SOC, HLT, HLT and PT	By the internationally agreed SOC order and by alphabetic order of HLTs, HLTs and PTs.
SOC, HLT and PT	By the internationally agreed SOC order and by alphabetic order of HLTs and PTs.
SOC and PT	By the internationally agreed SOC order and decreasing frequency of PTs ^{a, b}
SMQ/CMQ and PT	By decreasing frequency of SMQs/CMQs and PTs ^a

AE presentation	Sorting rules
PT	By decreasing frequency of PTs ^a

^a Sorting will be based on the SAR231893 dupilumab group
^b The table of all TEAEs presented by SOC and PT will define the presentation order for all other tables (eg, treatment-emergent SAE) presented by SOC and PT, unless otherwise specified.

Analysis of all adverse events

The overview of TEAE with the details below will be generated:

- Any TEAE
- Any severe TEAE
- Any treatment emergent SAE
- TEAE leading to death
- Any TEAE leading to permanent intervention discontinuation
- Any treatment emergent AESI
- Any treatment emergent other AE of interest grouping
- Any TEAE related to IMP

The AE summaries of [Table 7](#) will be generated with number (%) of participants experiencing at least one event.

Table 7 - Analyses of adverse events

Type of AE	MedDRA levels
All TEAE	Primary SOC, HLGT, HLT and PT
	Primary SOC and PT
	PT
	Primary and secondary SOC, HLGT, HLT and PT
Common TEAE ($\geq 2\%$ and 5% in any group)	Primary SOC and PT
TEAE related to IMP as per Investigator's judgment	Primary SOC, HLGT, HLT and PT
	Primary SOC and PT
TEAE by maximal intensity	Primary SOC and PT
Treatment emergent SAE	Primary SOC, HLGT, HLT and PT
	Primary SOC and PT
Treatment emergent SAE related to IMP as per Investigator's judgment	Primary SOC, HLGT, HLT and PT
TEAE leading to permanent intervention discontinuation	Primary SOC, HLGT, HLT and PT
	Primary SOC and PT
TEAE leading to death (death as an outcome of the AE as reported by the Investigator in the AE page)	Primary SOC, HLGT, HLT and PT

Type of AE	MedDRA levels
Pretreatment AE	Overview ^a
	Primary SOC and PT

^a Will include the following AE categories: any AEs, any serious AEs, any AEs leading to death, any AEs leading to permanent intervention discontinuation

Analysis of deaths

In addition to the analyses of deaths included in [Table 6](#) the number (%) of participants in the following categories will be provided:

- Deaths during the treatment-emergent and post-treatment periods
- Deaths in non-randomized or randomized but not treated participants.

Analysis of adverse events of special interest (AESIs) and other AEs of interest

Adverse events of special interest (AESIs) and other AEs of interest will be selected for analyses as indicated in [Table 8](#). Number (%) of participants experiencing at least one event will be provided for each event of interest. Tables will be sorted as indicated in [Table 6](#).

Table 8 - Selections for AESIs and other AEs of interest

AE Grouping	Criteria
AESI	
Anaphylactic reaction	Anaphylactic reaction algorithmic approach (Introductory Guide for Standardised MedDRA Queries (SMQs) Version 18.1): includes anaphylactic reaction narrow SMQ (20000021) terms and programmatic identification of cases based on occurrence of at least two preferred terms meeting the algorithm criteria occurring within 24 hours of each other. The latter cases identified using the algorithm will undergo blinded medical review taking into account the timing of events relative to each other and to IMP administration for final determination of an anaphylactic reaction or not.
Systemic hypersensitivity reactions	SMQ [20000214] hypersensitivity narrow search and [AE corrective treatment/therapy='Y' or Action taken with IMP='Drug withdrawn' or Action taken with IMP='Drug interrupted'] followed by blinded medical review (documented process) for selection of relevant systemic hypersensitivity events
Helminthic infections	CMQ10544 based on HLGT as "Helminthic disorder"
Any severe type of conjunctivitis	CMQ10498 based on PTs (See Section 5.6) ^a and "Severe" ticked in Adverse Events eCRF page
Any severe type of blepharitis	CMQ10497 based on HLGT as "Lid, lash and lacrimal infections, irritations and inflammations" and "Severe" ticked in Adverse Events eCRF page
Keratitis	CMQ10642 based on the following PTs [keratitis, allergic keratitis, ulcerative keratitis, atopic keratoconjunctivitis, herpes ophthalmic, ophthalmic herpes simplex, corneal infection] ^a
Clinically symptomatic eosinophilia (or eosinophilia associated with clinical symptoms) ^b	CMQ10641 based on HLGT = Eosinophilic disorders or PT=Eosinophil count increased

AE Grouping	Criteria
Pregnancy of a female participants entered in a study as well as pregnancy occurring in a female partner of a male participant entered in a study with IMP/NIMP	“Pregnancy” or “Partner Pregnancy” checked on the Pregnancy eCRF page as reported by the investigator
Significant ALT elevation	“ALT increase” and AESI answer “Yes” checked on AE eCRF as reported by the investigator (ALT >5 x ULN in participants with baseline ALT ≤2 x ULN; OR ALT >8 x ULN if baseline ALT >2 x ULN)
Symptomatic overdose with IMP	Symptomatic Overdose is answered Yes, with Overdose of IMP answered Yes on AE eCRF.
Symptomatic overdose with NIMP	Symptomatic Overdose is answered Yes, with Overdose of NIMP answered Yes on AE eCRF.
Other selected AE Grouping	
Serious injection site reactions or severe injection site reactions that last longer than 24 hours	HLT = ‘Injection site reaction’ and either with serious status, or with severe status and (AE end date/time - AE start date/time) ≥24 hours or ongoing
Severe or serious infection	Primary SOC = ‘Infections and infestations’ and with severe or serious status
Drug-related hepatic disorder	SMQ [20000006] Drug-related hepatic disorders- narrow
Injection site reaction	HLT = ‘Injection site reaction’
Malignancy	SMQ [20000091]- Malignant or unspecified tumors narrow
Suicidal behavior	CMQ10639 based on the following PTs [Completed suicide, Suicidal ideation, Depression suicidal, Suicidal behavior, Suicide attempt] ^a
Conjunctivitis (narrow)	CMQ10644 based on the following PTs [Conjunctivitis, Conjunctivitis allergic, Conjunctivitis bacterial, Conjunctivitis viral, Atopic keratoconjunctivitis] ^a
Conjunctivitis (broad)	CMQ10645 based on the following PTs [Conjunctivitis, Conjunctivitis allergic, Conjunctivitis bacterial, Conjunctivitis viral, Atopic keratoconjunctivitis, Blepharitis, Dry eye, Eye irritation, Eye pruritus, Lacrimation increased, Eye discharge, Foreign body sensation in eyes, Photophobia, Xerophthalmia, Ocular hyperaemia, Conjunctival hyperaemia] ^a
Conjunctivitis (FDA) ^c	CMQ10643 based on the following PTs [Conjunctivitis, Conjunctivitis allergic, Conjunctivitis bacterial, Conjunctivitis viral, Eye irritation, Eye inflammation, Giant papillary conjunctivitis] ^a
Keratitis (FDA) ^c	CMQ30102 based on the following PTs in (keratitis, ulcerative keratitis, allergic keratitis, atopic keratoconjunctivitis, and ophthalmic herpes simplex)

a The list of terms may be adjusted according to MedDRA version changes

b All cases of Eosinophilia will be included in the analysis, where cases associated with clinical symptoms will be further described in the CSR

c FDA requested for US labeling

The following summaries will be provided:

- All TEAEs, by selected standardized MedDRA query (SMQ)/Customized MedDRA query (CMQ) and PT or by laboratory values (as in alanine aminotransferase (ALT) elevation), showing the number (%) of participants with at least 1 PT,
- For each AESI and other selected AE groupings,
 - Number (%) of participants with any specific TEAE
 - Number (%) of participants with any specific serious AE (regardless of treatment emergent status)
 - Number (%) of participants with any specific treatment emergent serious AE
 - Number (%) of participants with any specific AE leading to death
 - Number (%) of participants with any specific TEAE leading to permanent study drug discontinuation
 - Number (%) of participants with any specific TEAE related to IMP reported by investigator
 - Number (%) of participants with any specific TEAE by maximum intensity, corrective treatment, and final outcome
 - Number of any specific TEAE adjusted by the exposure duration
 - Number of participants with any specific TEAE adjusted by the exposure duration at risk. For each specific TEAE, Kaplan-Meier estimates of cumulative incidence at Week 12, and 24 and K-M plot may be provided to depict the course of onset over time if the number of events is large enough.
 - Number (%) of participants with injection site reactions by IMP injection.
 - Number (%) of participants with different number of injection site reactions.
- In addition, AESIs reported by the investigator in eCRF will be summarized separately.

In addition, the exposure-adjusted adverse event incidence rate tables will provide the number of patients with at least 1 event per 100 patient-years for the summaries of TEAEs, treatment emergent SAE, TEAE leading to permanent intervention discontinuation, and AESIs and other selected AE groups in [Table 8](#).

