8.3 ADVERSE EVENTS AND SERIOUS ADVERSE EVENTS

Adverse event of special interest

An AESI is an AE (serious or nonserious) of scientific and medical concern specific to the Sponsor's product or program, for which ongoing monitoring and immediate notification by the Investigator to the Sponsor is required. Such events may require further investigation in order to characterize and understand them. Adverse events of special interest may be added, modified or removed during a study by protocol amendment.

For these AESIs, the Sponsor will be informed immediately (ie, within 24 hours), per SAE notification described in [Section 10.3](#), even if not fulfilling a seriousness criterion, using the corresponding pages in the CRF (to be sent) or screens in the eCRF. If an SAE or any AESI of anaphylactic reactions or systemic allergic reactions that are related to IMP and require treatment, or severe injection site reactions lasting longer than 24 hours, occurs in a participant, blood samples should be collected for determination of functional dupilumab concentration, and ADA assessment at or near the onset and completion of the occurrence of the event, if possible.

- Anaphylactic reactions.
- Systemic hypersensitivity reactions.
- Helminthic infections.
- Any severe type of conjunctivitis or blepharitis.
- Keratitis.

- Clinically symptomatic eosinophilia (or eosinophilia associated with clinical symptoms).
- Pregnancy of a female subject entered in a study as well as pregnancy occurring in a female partner of a male subject entered in a study with IMP/NIMP;
 - Pregnancy occurring in a female participant entered in the clinical trial or in a female partner of a male participant entered in the clinical trial. It will be qualified as an SAE only if it fulfills one of the seriousness criteria,
 - In the event of pregnancy in a female participant, IMP should be discontinued,
 - Follow-up of the pregnancy in a female participant or in a female partner of a male participant is mandatory until the outcome has been determined,
 - Abnormal pregnancy outcomes (eg, spontaneous abortion, fetal death, stillbirth, congenital anomalies, ectopic pregnancy) are considered SAEs.
- Significant ALT elevation
 - ALT >5 x ULN in participants with baseline ALT ≤ 2 x ULN;
OR
 - ALT >8 x ULN if baseline ALT >2 x ULN.
- Symptomatic overdose (serious or nonserious) with IMP/NIMP

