8.4 TREATMENT OF OVERDOSE

Overdose is an AESI (defined in [Section 8.3](#)). No antidote is available for dupilumab. Sponsor does not recommend specific treatment for an overdose.

In the event of an overdose, the Investigator/treating physician should:

1. Provide symptomatic care.
2. Contact the Medical Monitor immediately.
3. Closely monitor the participant for any AE/SAE and laboratory abnormalities until dupilumab can no longer be detected systemically.
4. Obtain a plasma sample for PK analysis as soon as possible if requested by the Medical Monitor (determined on a case-by-case basis).
5. Document appropriately in the CRF.

Decisions regarding dose interruptions will be made by the Investigator in consultation with the Medical Monitor based on the clinical evaluation of the participant.

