- An AE is any untoward medical occurrence in a patient or clinical study participant, temporally associated with the use of study intervention, whether or not considered related to the study intervention.

NOTE: An AE can therefore be any unfavorable and unintended sign (including an abnormal laboratory finding), symptom, or disease (new or exacerbated) temporally associated with the use of study intervention.

Events meeting the AE definition

- Any abnormal laboratory test results (hematology, clinical chemistry, or urinalysis) or other safety assessments (eg, ECG, radiological scans, vital signs measurements), including those that worsen from baseline, considered clinically significant in the medical and scientific judgment of the Investigator (ie, not related to progression of underlying disease).
- Exacerbation of a chronic or intermittent pre-existing condition including either an increase in frequency and/or intensity of the condition.
- New conditions detected or diagnosed after study intervention administration even though it may have been present before the start of the study.
- Signs, symptoms, or the clinical sequelae of a suspected drug-drug interaction.
- Signs, symptoms, or the clinical sequelae of a suspected overdose of either study intervention or a concomitant medication.
- “Lack of efficacy” or “failure of expected pharmacological action” per se will not be reported as an AE or SAE. Such instances will be captured in the efficacy assessments. However, the signs, symptoms, and/or clinical sequelae resulting from lack of efficacy will be reported as AE or SAE if they fulfil the definition of an AE or SAE.

Events NOT meeting the AE definition

- Any clinically significant abnormal laboratory findings or other abnormal safety assessments which are associated with the underlying disease, unless judged by the Investigator to be more severe than expected for the participant’s condition.
- The disease/disorder being studied or expected progression, signs, or symptoms of the disease/disorder being studied, unless more severe than expected for the participant’s condition.
- Medical or surgical procedure (eg, endoscopy, appendectomy): the condition that leads to the procedure is the AE.
- Situations in which an untoward medical occurrence did not occur (social and/or convenience admission to a hospital).

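### SAP Table 8 counts every eosinophilia adverse event in an AESI row labelled symptomatic, so that row and the overall AESI count can exceed the AESIs the protocol defines

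*SAP*

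**What the plan says.** **Eosinophilia.** The AESI list in Protocol 8.3 contains "Clinically symptomatic eosinophilia (or eosinophilia associated with clinical symptoms"). SAP Table 8 uses the same row title, and its criterion is "CMQ10641 based on HLGT = Eosinophilic disorders or PT=Eosinophil count increased". There is no symptom condition. Footnote b confirms the scope: "All cases of Eosinophilia will be included in the analysis, where cases associated with clinical symptoms will be further described in the CSR".

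**ALT.** Protocol 8.3 sets the AESI at ALT above 5 x ULN when baseline is at most 2 x ULN, and above 8 x ULN when baseline is higher. Table 8 prints the same thresholds but selects the case by the AESI answer "checked on AE eCRF as reported by the investigator". The list of summaries under the table speaks of presenting events "by laboratory values (as in alanine aminotransferase (ALT) elevation").

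**Overdose.** Protocol 8.3 lists symptomatic overdose with IMP or NIMP, and Table 8 selects exactly that. SAP 4.7.1 takes cases of at least twice the intended dose in less than 11 days, with no symptom condition, and says they "will be considered an AESI per dupilumab clinical programs and will be listed as such". Protocol 8.4 says "Overdose is an AESI" and refers back to 8.3 for the definition.

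**The concern.** SAP 4.7.2 says that AESIs are selected as Table 8 indicates. Any widening of a Table 8 row therefore carries into the any-AESI line of the TEAE overview, into the by-event summaries and into the exposure-adjusted incidence rates, all of which draw on the same selection.

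For eosinophilia, the row title and the row content differ. A reader of the study report would take the count as symptomatic eosinophilia, when it is all reported eosinophilia. Table 8 offers no separate count of symptomatic cases, no criterion for symptomatic, and no blinded review of these cases.

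The direction of the excess is foreseeable, though its size is not. Protocol 2.3 names eosinophilia among the identified adverse reactions to dupilumab, and the schedule of activities draws hematology at every visit. Symptom-free rises can therefore be seen, and may be seen more often on dupilumab. With about 75 participants per arm, AESI totals may be small enough for one or two extra cases to show.

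**Working it through.** The documents state no AESI count or rate, so there is no figure to reproduce. The check is a comparison of definitions, followed by an illustration with assumed rates.

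**Definitions side by side**

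| Event | Protocol 8.3 | SAP Table 8 | Elsewhere | Result |
|---|---|---|---|---|
| Eosinophilia | Symptomatic only | All eosinophilia AE terms (footnote b) | – | Table 8 is broader than the protocol |
| ALT | >5 x ULN, or >8 x ULN if baseline >2 x ULN | Same thresholds, found by investigator tick | Text under Table 8: laboratory values | Same definition, source not settled |
| Overdose | Symptomatic | Symptomatic | SAP 4.7.1: no symptom condition; Protocol 8.4: not restated, refers to 8.3 | Table 8 agrees with 8.3; 4.7.1 does not |

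**What limits the eosinophilia excess.** An abnormal laboratory result is an adverse event under Protocol Appendix 3 only if it is "considered clinically significant in the medical and scientific judgment of the Investigator". A raised count that the investigator does not report as an adverse event never reaches Table 8. The excess is therefore the number of participants with a reported, symptom-free eosinophilia event and no other AESI.

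**Illustration.** Take n = 75 per arm (SAP 1.1). Let a be the share with a protocol-defined AESI and b the share with a symptom-free eosinophilia event. Both are assumptions, taken as independent.

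- Share in the any-AESI line = 1 − (1 − a)(1 − b). With a = b = 3%: 1 − 0.97 × 0.97 = 0.0591, and 75 × 0.0591 = 4.43 participants, against 75 × 0.03 = 2.25 under the protocol definition.
- Chance of at least one symptom-free case in an arm = 1 − (1 − b)^75.

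| a (participants) | b = 0 | b = 1% | b = 3% | b = 5% |
|---|---|---|---|---|
| 1% (0.75) | 0.75 | 1.49 | 2.98 | 4.46 |
| 3% (2.25) | 2.25 | 2.98 | 4.43 | 5.89 |
| 5% (3.75) | 3.75 | 4.46 | 5.89 | 7.31 |
| Chance of ≥1 symptom-free case | 0 | 53% | 90% | 98% |

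If b were 3% on dupilumab and 0 to 1% on placebo, the eosinophilia row would gain 75 × 0.03 = 2.25 participants against 0 to 0.75.

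**ALT cross-check.** SAP 4.7.3.1 summarizes ALT above 3, 5, 10 and 20 x ULN. Both protocol thresholds are at least 5 x ULN, so the >5 category contains every protocol-defined elevation. It also contains participants with baseline above 2 x ULN whose peak lies between 5 and 8 x ULN, who are not AESIs. With no >8 category and no split by baseline, it bounds the protocol count from above but does not reproduce it.

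**The case against.** The strongest case on the other side is that this is a disclosed presentation choice. Footnote b states openly what is counted. The wider row errs towards showing more events and does not hide risk. SAP 4.7.2 also plans a separate summary of AESIs as reported by the investigator, which should follow the protocol's classification. AESI incidence is not an endpoint: the safety endpoint is the percentage with TEAEs or SAEs, which does not depend on Table 8. SAP 4.7 makes safety descriptive, with no testing.

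Most of this stands, and it keeps the point small. It does not remove it. The separate summary leaves the Table 8 row, the overview line and the exposure-adjusted rates as they are, and a footnote does not change a row title that says symptomatic.

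A reader might also infer three stronger things that the documents do not support.

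- *That Table 8 drops overdoses the protocol defines as AESIs.* It does not. Table 8 matches the Protocol 8.3 list, and Protocol 8.4 points back to that list. The conflict is SAP 4.7.1 against Table 8, with loose wording in Protocol 8.4. Overdoses meeting the 4.7.1 definition are in any case to be listed.
- *That the ALT row uses a different definition.* It prints the protocol thresholds, and Protocol 8.3 makes investigator notification the route for every AESI. The same thresholds appear in Protocol 7.1.1 among the reasons for permanent withdrawal from treatment, so such a result is unlikely to pass unnoticed. What remains is the risk of a missed tick and an unstated source.
- *That the overall AESI count is simply wrong.* It departs from the protocol only if a symptom-free eosinophilia case is reported as an adverse event, or through a missed ALT tick. Neither can be predicted from the documents.

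**Conclusion.** The eosinophilia point holds. Applied as written, Table 8 puts symptom-free cases into a row titled symptomatic. The row, the any-AESI line and the exposure-adjusted AESI rates can then exceed the protocol-defined count. The excess cannot be sized from the documents. It is zero if no symptom-free case is reported as an adverse event, and about 2 participants in an arm of 75 at an assumed rate of 3%. An excess concentrated on dupilumab is plausible from Protocol 2.3, but no rate in the documents shows it. The investigator-reported summary is a partial offset.

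The ALT and overdose items are secondary. For ALT, the SAP names two sources and does not say which drives the count; a missed tick could only lower it. For overdose, the passages disagree on whether symptoms are required, but Table 8 itself does not depart from Protocol 8.3. Neither effect can be quantified. No hypothesis test, error rate or sample size depends on any of the three, so this is a minor point worth correcting because it is cheap.

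**What to change.** Before the primary database lock, amend SAP 4.7.2 and Table 8 as follows.

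1. Restrict the eosinophilia AESI row, and its contribution to the any-AESI line and the exposure-adjusted AESI rates, to symptomatic cases. Identify them by the investigator's AESI classification or by blinded medical review, which Table 8 already uses for algorithm-identified anaphylaxis and for systemic hypersensitivity. Say which of the two is used.
2. Show all eosinophilia events under the other selected AE groupings. Table 8 already has this layout for conjunctivitis: a restricted AESI row, with broader groupings below. Footnote b then moves to the broader row.
3. State that the ALT AESI is derived from laboratory values with the protocol's baseline-dependent thresholds, together with cases the investigator ticked.
4. Reconcile SAP 4.7.1 and Protocol 8.4 with Protocol 8.3 and Table 8 on whether symptom-free overdose is an AESI, and use one wording throughout.

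The cost is SAP wording, one more table row, a short review of what are probably few eosinophilia cases, and a programmed ALT flag from data already collected. If Protocol 8.4 is reworded, that needs a minor clarification there. No new data collection is required.
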